10.1.5 Post-Operative Follow-Up Visits (Visit 4-8)

Post-operative visits 4-8 for oncologic subjects will be made via a phone call to assess overall survival, progression-free survival, and disease-free survival.

Medtronic Expand URO Clinical Investigation Plan

MDT19051EINURO

Version 9.0

Page 40 of 111

Medtronic

Table 6. Data Collection and Study Procedure Requirements at Subject Visits

Procedure/Assessment	Screening (Day -30 to 0) Visit 1	Surgical Procedure (Day 0) Visit 2	Hospital Discharge Visit 2.1	Follow-Up (30+7 Days) Visit 3	Follow-up (Years 1 - 5) (+/- 3 mo. window) Visits 4-8
	May be Combined				
Informed Consent Form ¹	X	X			
Eligibility Criteria	X	X			
Demographic Data	X				
Medical/Surgical History	X				
Concomitant Medication(s)	X	X	X	X	
Lab Values (if applicable)	X	X	X	X	
Robot Setup Time		X			
Total Operative Time (skin to skin)		X			
Surgeon Console Time		X			
Instruments Used		X			
Estimated Blood Loss		X			
Transfusion ³		X	X	X	
Conversion to a robotic-assisted approach utilizing an FDA cleared robotic-assisted device, open or manual laparoscopy		X			
Robot Take Down Time		X			
Warm Ischemia Time (if applicable)		X			
Anastomotic Leak Test performed (if applicable)		X			
Anastomotic Stricture (if applicable)		X			
Rate of Positive Circumferential Margins on Final Pathology (if applicable)		X			
Margin (mm) (if applicable)			X		

Medtronic Business Restricted

This document is electronically controlled

CONFIDENTIAL 056-F275 Rev E Clinical Investigation Plan Template

Medtronic Expand URO Clinical Investigation Plan

MDT19051EINURO

Version 9.0

Page 41 of 111

Medtronic

Procedure/Assessment	Screening (Day -30 to 0) Visit 1	Surgical Procedure (Day 0) Visit 2	Hospital Discharge Visit 2.1	Follow-Up (30+7 Days) Visit 3	Follow-up (Years 1 - 5) (+/- 3 mo. window) Visits 4-8
Tumor Size (if applicable)			X		
Tumor Stage (if applicable)			X		
Total number of lymph nodes retrieved			X		
Catheterization Time			X	X	
Mortality			X	X	X
Length of Hospital Stay			X		
Reoperation			X	X	X
Pain Medication			X	X	
Medications if associated with an AE	X	X	X	X	X
Adverse Events ²	X	X	X	X	X
Readmission				X	X
Device Accountability		X			
Device Deficiency		X			
Protocol Deviation Collection (if applicable)	X	X	X	X	X
Study Exit				X	X

¹Study specific procedures may only be performed after subject has agreed to participate and signed the informed consent form.

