8	Reoperation Rate	Reoperation through 30 days is identified in a subject if they experience a related (device, procedure, or underlying condition/disease) adverse event that resulted in treatment with a surgical procedure and the AE start date was prior to or during the 30-calendar days post-procedure.
9	Mortality Rate	Death through 30 days is identified as an AE that led to death which occurs during the procedure or up to the 30 calendar-days post-procedure.
10	Device Deficiencies	A subject is identified as experiencing a device deficiency if a device deficiency occurred before, during, or after the subject's procedure.
11	Overall Survival	Subject death will be identified as an adverse event that leads to death where the adverse event start date is on or after the procedure date or if the subject is noted by the site to have died during follow-up. Time to death will be calculated as the difference in days between death and the procedure date.
12	Progression-free Survival	Disease progression will be identified in a subject if their disease state is noted by the site, during follow-up, as "disease reoccurrence, disease progression", or if subject death had been noted. This is assessed as either at the time of the follow-up visit or at the time of last contact, whichever is earlier will be denoted as the time of disease

		progression. Time to disease progression is calculated as the difference in days between disease regression and the procedure date.
13	Disease-free Survival	Disease reoccurrence will be identified in a subject if the subject disease state is noted by the site, during follow-up, as “disease reoccurrence, disease progression”, “disease reoccurrence, disease stable”, or if subject death had been noted. This is assessed either at the time of a follow-up visit or at the time of last contact, whichever is earlier will be denoted as the time of disease reoccurrence. Time to disease reoccurrence will be calculated as the difference in days between disease reoccurrence date and the procedure date.

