7.9.3.5 Analysis Methods

Secondary objectives 1, 4, 5, 7, 8, 9 and 10 will be summarized by surgery as the count and proportion of subjects experiencing the given endpoint, with a 95% confidence interval.

Secondary objectives 2, 3 and 6 will be summarized by surgery performed using mean, standard deviations (SD), median, IQR, and range. A 95% confidence interval will also be calculated.

Secondary objectives 11, 12 and 13 will be evaluated through separate Kaplan-Meier analyses by surgery.² The event for each Kaplan-Meier will be their respective objective endpoint. Subjects will be censored upon study completion (5-year follow-up visit) or they are lost to follow-up without event. For subjects that are lost to follow-up, their last visit date or date of last subject contact will be used as their censor date, whichever occurred later. The 5-year survival will be estimated from the Kaplan-Meier model and a 95% confidence interval will be calculated.

Secondary objective 1 will have three additional exploratory analyses wherein the overall complication rate within 30 days will be limited to each of: related to device, related to procedure, and related to underlying condition. Relatedness in this exploratory analysis will be any rating other than “Not Related” or equivalent.

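### PFS and DFS count deaths as events but date them at a phone visit or last contact, so the same death gets a different time than in overall survival

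*SAP*

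**What the plan says.** In SAP 7.9.3.1, endpoint 11 (overall survival) is measured to the death: "Time to death will be calculated as the difference in days between death and the procedure date".

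Endpoint 12 (PFS) takes as its event a site report of progression, or a death, and then gives one dating rule for the whole event set: "if subject death had been noted. This is assessed as either at the time of the follow-up visit or at the time of last contact", with "whichever is earlier will be denoted as the time of disease" progression. Endpoint 13 (DFS) also includes deaths and follows the same rule: "This is assessed either at the time of a follow-up visit or at the time of last contact", again taking the earlier. The last sentence of endpoint 12 measures time to disease regression, where progression is evidently meant.

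SAP 7.9.3.5 uses Kaplan-Meier by surgery type and reports a 5-year estimate. On censoring it says: "Subjects will be censored upon study completion (5-year follow-up visit) or they are lost to follow-up without event". For lost subjects, "their last visit date or date of last subject contact will be used as their censor date, whichever occurred later".

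Protocol 10.1.5 sets the contact pattern: "Post-operative visits 4-8 for oncologic subjects will be made via a phone call to assess overall survival", PFS and DFS. Table 6 gives the timing as "Follow-up (Years 1 - 5) (+/- 3 mo. window". Protocol 12.6 lists the date of death among the data collected for every death.

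**The concern.** PFS and DFS are composites that include every death. For a subject whose only event is death, all three endpoints should therefore have the same time. As written they do not: OS uses the date of death, and the other two use a contact date that may lie many months away. If the contact is the later visit, the PFS curve can sit above the OS curve, which is impossible for a composite that contains every OS event. A programmer also cannot tell which date applies when a death is learned of at one call and the previous contact was a year before.

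At stake are two pre-specified long-term endpoints that have performance goals in Protocol 14.5 and appear in the 5-year final report. The SAP does not name the month at which the 5-year value is read, and the year-5 call may fall anywhere from month 57 to month 63. The dating rule therefore interacts with the reading point.

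**Working it through.** The documents give no expected event count or Kaplan-Meier value that depends on the dating rule, so there is no planned figure to reproduce.

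**Step 1: one death, three endpoints.** Death at month 50, calls at months 48 and 60.

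| Endpoint | Date used | Time (months) |
|---|---|---|
| OS | death | 50 |
| PFS, DFS, if the reporting visit is used | visit | 60 |
| PFS, DFS, if the last contact is used | last contact | 48 |

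This conflict needs no assumption.

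**Step 2: inputs for size.** From the documents: yearly calls in years 1 to 5 within 3 months either side (Protocol Table 6); censoring of event-free subjects at the year-5 call (SAP 7.9.3.5); literature 5-year OS means of 0.954 (prostatectomy), 0.931 (nephrectomy) and 0.645 (cystectomy) (Protocol 14.5). Assumed: constant hazard, call dates uniform within the window, no other dropout, and all events treated as deaths so that a correctly dated PFS equals OS. The OS means are illustrations only, because Protocol 14.5 says 5-year PFS and DFS are not reported in the literature. Rates of 0.35 and 0.10 are added to cover lower event-free survival.

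**Step 3: month 60 by hand, at 0.645.**

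- Monthly hazard h = -ln(0.645)/60 = 0.00731, and S(48) = exp(-48h) = 0.704.
- *Visit dating.* Events up to the year-4 call are all on the curve by month 51, which then stands at about 0.704. Year-5 calls arrive uniformly over months 57 to 63, so the hazard of being called at month u is 1/(63 - u). A fraction q of those calls reports an event.
- The curve at month 60 is then 0.704 × exp(-q ∫ du/(63 - u), from 57 to 60) = 0.704 × exp(-q ln 2) = 0.704 × 2^(-q).
- The weighted mean call month up to 60 is 63 - 3/ln 2 = 58.67, which is 10.67 months after month 48. So q = 1 - exp(-0.00731 × 10.67) = 0.075.
- Result: 0.704 × 2^(-0.075) = 0.704 × 0.949 = 0.668, a shift of 0.668 - 0.645 = +2.3 points.
- *Last-contact dating.* Events between the year-4 and year-5 calls are all dated at the year-4 call. The curve is then already down to the proportion event-free at the year-5 call, on average S(60) = 0.645. The shift is 0.

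**Step 4: simulation, 400,000 subjects per row, month 60.**

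| 5-year rate | Dated at event | Dated at visit | Dated at last contact |
|---|---|---|---|
| 0.954 | 0.954 | 0.957 | 0.954 |
| 0.931 | 0.932 | 0.937 | 0.932 |
| 0.645 | 0.645 | 0.668 | 0.645 |
| 0.35 | 0.350 | 0.384 | 0.350 |
| 0.10 | 0.100 | 0.126 | 0.100 |

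The third row agrees with the hand calculation. In that scenario events are dated on average 6.3 months late (visit) or 5.9 months early (last contact), and at most about 18 months off.

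**Step 5: away from month 60, at 0.645.** At month 36 the true value is 0.768; visit dating gives 0.807 (+3.9 points) and last-contact dating 0.732 (-3.6 points). At month 63, under visit dating, the integral in step 3 grows without limit: a year's events are placed on call dates while event-free subjects are being censored on those same dates. The result then depends on sample size. With 31 subjects, the cystectomy cap, and all of them assumed oncologic, it averages about 0.49 against about 0.63 when correctly dated.

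**Step 6: scale.** The binomial standard error for 31 subjects at 0.645 is √(0.645 × 0.355/31) = 0.086, or 8.6 points.

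**The case against.** The strongest reply is that the effect at month 60 is small: zero under last-contact dating, 0.3 to 0.5 points under visit dating at the prostatectomy and nephrectomy means, and 2.3 points at the cystectomy mean, against a standard error of 8.6 points. That stands.

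A second reply is that dating progression or recurrence when it is first detected is a usual convention, since onset between yearly calls is not observed. That also stands, so midpoint imputation or interval-censored estimation would be a preference rather than a correction. It does not cover deaths, whose dates are collected.

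A third reply is that the rule speaks of the time of progression or recurrence and may never have been meant to date deaths. That is possible, but the text puts deaths in the event set and offers no other date for them.

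A reader might also infer that taking the earlier date for events and the later date for censoring is itself an error. The documents do not support that. The later-date rule applies to lost subjects without an event, and censoring them at the latest event-free contact is sound. Whether a death could be dated before a contact at which the subject was known to be alive depends on which visit the rule means, so that is a matter for clarification.

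**Conclusion.** As written, the rule gives one death two different times across endpoints that should agree, and it allows PFS to exceed OS. That conclusion rests on the text alone. Its numerical effect rests on the assumptions in the working: 0 to about +2.3 points at month 60 with the 64.5% illustration, about +3.4 points at a 35% rate, about 4 points either way mid-curve, and much more if the curve is read near month 63 under visit dating.

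A reader might go further and conclude that the 5-year estimates are simply wrong, or 3 to 6 points too high. The 6-point figure is S(48) - 0.645 = 0.704 - 0.645, which needs every year-5 event still undated when the curve is read. The window is symmetric around month 60 and the rule names the earlier date, so the documents do not support it.

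PFS and DFS are descriptive, with benchmark goals and no test, and study success rests on the primary endpoints. No primary conclusion changes. The wording should still be corrected, because a descriptive estimate also needs a defined event time.

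**What to change.** In SAP 7.9.3.1 and 7.9.3.5:

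- Date deaths at the date of death in PFS and DFS, as in OS.
- Date progression or recurrence at its documented date where available, otherwise at the contact where it was first reported.
- State that the 5-year Kaplan-Meier estimate is read at month 60.
- In endpoint 12, replace regression with progression in the time calculation.

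The censoring rule can stay. The cost is a few lines of SAP wording. The case report form is not among the documents, so it cannot be seen whether a progression or recurrence date is already collected. If it is not, one date field would be needed on the yearly follow-up form, and it is best added early because a date not asked for at the call may be hard to recover later.

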7.9.3.2 Hypotheses

Secondary objectives are not powered for statistical significance, no hypothesis testing will take place.

7.9.3.3 Performance Requirements

Performance goals for each of the secondary objectives can be found in **Section 10**.

7.9.3.4 Rational for Performance Criteria

Rationale for each of the performance goals for secondary objectives can be found in **Section 10**.

7.9.3.5 Analysis Methods

Secondary objectives 1, 4, 5, 7, 8, 9 and 10 will be summarized by surgery as the count and proportion of subjects experiencing the given endpoint, with a 95% confidence interval.

Secondary objectives 2, 3 and 6 will be summarized by surgery performed using mean, standard deviations (SD), median, IQR, and range. A 95% confidence interval will also be calculated.

Secondary objectives 11, 12 and 13 will be evaluated through separate Kaplan-Meier analyses by surgery.² The event for each Kaplan-Meier will be their respective objective endpoint. Subjects will be censored upon study completion (5-year follow-up visit) or they are lost to follow-up without event. For subjects that are lost to follow-up, their last visit date or date of last subject contact will be used as their censor date, whichever occurred later. The 5-year survival will be estimated from the Kaplan-Meier model and a 95% confidence interval will be calculated.

Secondary objective 1 will have three additional exploratory analyses wherein the overall complication rate within 30 days will be limited to each of: related to device, related to procedure, and related to underlying condition. Relatedness in this exploratory analysis will be any rating other than “Not Related” or equivalent.

7.9.3.6 Determination of Subjects/Data for Analysis

Subjects from the FAS with data available will be included for each secondary analysis. Secondary endpoint 2 will add the additional requirement that it will be for subjects who did not undergo conversion.

7.9.4 Ancillary Objectives

Descriptive analyses of ancillary objectives will be exploratory in nature and are not intended as a focus of the study for the evaluation of the study device.

7.9.4.1 Rate of Negative Surgical Margins

The surgical margin at the 30-day follow-up will be summarized. The positive margin rate and the margin, recorded for each oncological subject, will be summarized using mean (SD), median, minimum, and maximum in subjects from the FAS with complete data at the 30-day follow-up. A lower value for these outcomes will indicate a more positive outcome.

7.9.4.2 Lymph Node Yield

The proportion of lymph nodes suspected to contain cancer cells at the 30-days follow-up will be calculated as the total positive lymph nodes divided by the total number of lymph nodes retrieved. This proportion will be summarized using mean (SD), median, minimum, and maximum in oncological subjects from the FAS with complete data at the 30-day follow-up. A lower value for these outcomes will indicate a more positive outcome.

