5.1.5 Other Prespecified Outcomes Measures

Descriptive analyses of other pre-specified outcome measures beyond the primary and secondary objectives will be exploratory in nature and are not intended as a focus of the study for the evaluation of the study device.

The following will be collected as applicable:

- Rate of positive surgical margins
- Lymph node yield
- Warm ischemia time
- Surgeon experience

6. Study Design

A prospective, multicenter, single-arm pivotal study will be performed in up to 141 subjects undergoing a urologic RAS procedure using the Medtronic Hugo™ RAS System. Subjects without an oncologic indication will be followed for 30 days (+7 days) post procedure. Oncologic subjects will be followed through 5 years. This study will be conducted using up to six investigative sites in the United States of America (USA).

This study will have two phases, a roll-in phase and an open enrollment phase.

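### SAP 7.9.4.2 analyses node positivity under the name lymph node yield, and no summary of the number of nodes retrieved is specified

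*SAP*

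**What the plan says.** Protocol 5.1.5 lists "Lymph node yield" among the other prespecified outcome measures, and Protocol 14.6 and SAP 4.3 repeat it. None of these places gives a formula. Protocol Table 6 (under 10.1.5) schedules "Total number of lymph nodes retrieved"; it has no row for the number of positive nodes.

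The only definition is in SAP 7.9.4.2, under the heading for lymph node yield. It reads "The proportion of lymph nodes suspected to contain cancer cells at the 30-days follow-up will be calculated as" "total positive lymph nodes divided by the total number of lymph nodes retrieved". On reporting, it says "This proportion will be summarized using mean (SD), median, minimum, and maximum in oncological subjects from the FAS", limited to those with complete data at the 30-day follow-up. It closes with "A lower value for these outcomes will indicate a more positive outcome".

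On status, SAP 7.9.4 states: "Descriptive analyses of ancillary objectives will be exploratory in nature and are not intended as a focus of the study".

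**The concern.** Yield, in its ordinary sense, is how many nodes the surgeon removed. It bears on how extensive a dissection was achieved with the device. In the SAP's formula that number appears only as the denominator. The numerator depends on how much nodal disease the patient had and on whether the positive nodes were among those removed. A low value can therefore come from a node-negative patient, from a thorough dissection, or from a limited dissection that left positive nodes behind, and the ratio cannot tell these apart.

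If the SAP is followed as written, the study report will show a disease-burden measure labelled as surgical yield. The count that the label refers to will have no planned summary.

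**Working it through.** The plan gives no sample size, alpha, effect size or performance goal for this outcome, so there is no stated figure to reproduce. The check has three steps.

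**1. Name against formula.** The name in Protocol 5.1.5, Protocol 14.6 and SAP 4.3 is lymph node yield. The node variable in Table 6 is the total retrieved. The quantity in SAP 7.9.4.2 is r = x / n, with x the positive nodes and n the nodes retrieved, and only r is summarised. The count n is collected but has no specified summary. The count x is needed but has no row in Table 6. When n = 0, r is undefined, and the SAP does not say how such subjects are handled.

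**2. Worked examples** (illustrative counts, not from the documents; lower r is called better).

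| Limited dissection | Larger dissection | Favoured by r | Favoured by n |
|---|---|---|---|
| 0/4 = 0% | 2/20 = 10% | limited | larger |
| 1/3 = 33% | 1/20 = 5% | larger | larger |
| 1/5 = 20% | 2/20 = 10% | larger | larger |
| 0/3 = 0% | 0/20 = 0% | tie | larger |

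The count n orders the dissections by extent in every row. The ratio r does so in two of the four.

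**3. How often the order reverses.** Assumptions, none from the documents: 25 nodes present, K of them positive, nodes retrieved at random, and two independent subjects with 5 and 20 nodes retrieved. Then x is hypergeometric and E(x/n) = K/25 whatever n is.

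For K = 1, the probability of finding no positive node is 20/25 = 0.80 with 5 retrieved and 5/25 = 0.20 with 20 retrieved.
- The limited dissection scores lower when it misses the node and the larger one finds it: 0.80 × 0.80 = 0.64.
- The larger dissection scores lower whenever the limited one finds the node (1/5 = 20% against 0% or 5%): 0.20.
- The remainder, 0.80 × 0.20 = 0.16, is a tie at 0%.

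The same calculation for the other values of K gives:

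| K | Expected r, both dissections | Limited scores lower | Larger scores lower | Tie |
|---|---|---|---|---|
| 0 | 0 | 0 | 0 | 1 |
| 1 | 0.04 | 0.64 | 0.20 | 0.16 |
| 2 | 0.08 | 0.61 | 0.37 | 0.02 |
| 4 | 0.16 | 0.38 | 0.44 | 0.17 |

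Under these assumptions the mean ratio carries no information about how many nodes were removed. For an individual pair the order can go either way. It favours the limited dissection mainly when there are few positive nodes to miss.

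**The case against.** The case for leaving the plan alone has four parts.

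- **Direction.** For the proportion that SAP 7.9.4.2 defines, lower is the favourable direction, since fewer nodes contain cancer. This stands. A reader might infer that the sign is wrong, but that follows only if the count is substituted for the ratio, and the section does not do that. The fault is the label and the missing count.
- **Ranking.** A reader might infer that the measure would always place a poor dissection above a thorough one. The formula does not support that. With the same number of positive nodes, more nodes retrieved lowers the ratio, and node-negative subjects all tie at zero. What stands is that it can reverse the order.
- **General rules.** SAP 7.2 promises standard summaries of continuous study outcomes, and SAP 7.7 promises a description of surgical procedure characteristics. Neither names node count, and 7.9.4.2 is the specific provision for this outcome. They do not close the gap.
- **Status.** The outcome is exploratory, has no hypothesis and no performance goal in Protocol 14.5, and under Protocol 14.1 study success rests on the primary endpoints. This stands and limits the impact. It does not justify reporting one quantity under the name of another.

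**Conclusion.** The point holds as a mismatch between name and definition. SAP 7.9.4.2 specifies node positivity for an outcome called lymph node yield, and no summary of the number retrieved is specified, although that number is collected. The ratio mainly reflects disease burden, does not measure the extent of dissection, and can, though need not, favour a limited dissection.

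The 0/4 against 2/20 example needs no assumption beyond the formula. The reversal probabilities depend on the assumed 25 nodes, random retrieval and 5 against 20 nodes removed, and serve only to show that either order is possible.

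The impact is low. No primary or secondary result, sample size or alpha changes. A reader might also infer that the trial would use this ratio as evidence for or against the device. The documents do not support that, because they set the ancillary outcomes apart from the device evaluation.

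**What to change.** In SAP 7.9.4.2:

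- Define lymph node yield as the total number of nodes retrieved per subject, and summarise it descriptively (for example n, median, IQR and range). A split by surgery type and restriction to subjects with nodes retrieved are preferable; the restriction also removes the undefined case of zero retrieved.
- If node positivity is kept, report it separately under its own name as a disease characteristic, and delete the sentence saying that lower is better.
- Confirm that the case report form captures the number of positive nodes, since Table 6 does not list it. If it does not, positivity cannot be calculated as planned.

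The cost is a wording change to the SAP. Table 6 already schedules the count needed for yield. Only the separate positivity summary might need a further data item.
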